10.2.2 Secondary Outcome

One tailed t-tests for independent groups will be performed to test the hypothesis that participants using the active vs sham CES device will have smaller reductions in telomere length and higher telomerase levels at post compared to pre-treatment.

10.2.3 Exploratory Outcomes

- One tailed t-tests of independent groups will be performed to test the hypotheses that active CES device will be superior to sham in improvement of PROMIS domains, MHC-SF, CD-RISC, PSS, PHQPANAS-SF and impression of global improvement.

11 ETHICS/PROTECTION OF HUMAN SUBJECTS

11.1 Institutional Review Board

The protocol, Informed Consent Forms, recruitment materials, and all subject materials will be submitted to the IRB for review and approval. Approval of both the protocol and the Informed Consent Form must be obtained before any subject is enrolled. Any amendment to the protocol will require review and approval by the IRB before the changes are implemented in the study.

11.2 Informed Consent Process

Informed consent is a process that is initiated prior to the individual agreeing to participate in the study and continues throughout study participation. Before coming to the clinic, the study is explained via phone screening using the IRB-approved prescreening script. All interested volunteers are offered a copy of the consent form beforehand in order to review and ponder the consent by themselves or with family, friends or advisors before their screening date. At every stage of the process, they will be given opportunity to ask questions or voice concerns that they may have.

The informed consent and study documents will be in English language only therefore only persons fluent in reading English will be eligible to enroll into the study. The consent is written to ensure comprehension at a 6th-8th grade level. No vulnerable persons, as defined by the Office of Protection of Research Subjects (OPRS/IRB), will be targeted. The PI and research personnel (co-investigator, RNs, research assistant) will be responsible for inviting subjects to participate. The study will be explained in detail and they will be allowed as much time as needed to read, comprehend and ask any pertaining questions. After the subject has read the consent form at the UCLA OCNS private clinic exam room area, the investigator will review the study and answer any questions or concerns regarding participation. Subjects will be asked to summarize the information provided to ensure comprehension. It will be explained that they are allowed to withdraw consent at any time without retribution. The consent process will be documented in the research record.

11.3 Subject Confidentiality

Subject's names and study information will be kept on a password protected database, and will be linked only with a unique 4-digit study identification number for this research. The only people who will have access to the data or the codes will be research team associated with this study. All other data is stripped of personal identifiers and stored in an encrypted Microsoft Access database. All electronic data in the computer database is password protected. Paper source documents are stored in a locked office with locked cabinets in a secured office location. Only authorized research personnel will have access to the locked office and cabinets.

11.4 Future Use of Stored Specimens and Other Identifiable Data

These procedures will be taken to protect the confidentiality of the subjects who donate samples. The procedures by which samples will be stored including the information that will be attached to samples. The process by which the donor's identity will be protected (process of coding and de-identifying samples) including the location where the information that links a sample to the identity of the donor is kept and who has access to this information.

Although the samples containing genetic material will be coded and no subject identifiers will be attached to the samples, the codes will be maintained by the PI or the research assistant in the records along with the date of collection on the tube containing genetic material and in the specimen log book. This will allow protecting the identity of the donor from anybody who has access to the storage, but is not working on the study. The Samples will be coded but not anonymous. Therefore the policy will read:

Policy: Samples will be coded to protect the identity of the donor from anybody who is not a part of the research team. The link will be maintained between subject identifiers and stored samples in the PI's records. Samples will be stored in a manner that optimizes the viability of the specimen and the utility of the cells for research. All equipment used in preparation or storage of human specimens shall be subject to routine maintenance to ensure optimal preservation of specimens.

Process: The participant will specify within the consent form whether they would like to the samples stored for future research. On receipt of a sample the PI or study coordinator will assign a code to the sample and record the code and the date of collection on the tube containing genetic material and in the specimen logbook. This will be the only link between the samples and the subjects accessible only to the PI and members of the research team. The sample will then be processed in accordance with the research needs of the study. The samples will not be shared.

Sharing: The participant sample will not be shared with other researchers outside the research team. Since the sample will only be shared within the research team, the only set process for sharing (within the team) will be a written request to the PI. Only after approval by the PI, will the samples be release to the co-investigators. Only the subjects ID will accompany the sample.

Processing of sample upon leaving UCLA: In the event that the PI leaves UCLA, then the samples will be destroyed.

12 DATA HANDLING AND RECORD KEEPING

12.1 Data Management Responsibilities

Data collection and accurate documentation are the responsibility of the study staff under the supervision of the investigator. All source documents and laboratory reports must be reviewed by the study team and data entry staff, who will ensure that they are accurate and complete. Unanticipated problems and adverse events must be reviewed by the investigator.

12.2 Data Collection

Paper source documents with data collected at UCLA will be coded and kept in locked cabinets. A coding key and any collected identifiers (e.g., phone, address) will be kept in a separate locked cabinet by the PI. All data will be coded upon storing and before data analysis.

Electronic data collected at UCLA will be done using SurveyMonkey and will be coded. All data will be stripped of personal identifiers and stored in an encrypted Microsoft Access database. All data in the computer database will be password protected. Only authorized research personnel will have access to the password protected computer database.

12.3 Study Records Retention

Upon completion of the study, the coding key and all identifiers will be destroyed, rendering the data anonymous.

With subject permission, we may store specimen data with or without subject's name or identifying information for future use. Retention of blood specimens after the end of the study for use in future research must be granted permission from the subject on the ICF. Subjects will give permission on the ICF if they agree to keep their name and other identifying information with their specimens. See 11.4 for future use of stored specimens plan.

13 RESULTS:

13.1 Feasibility: This was a feasibility study, initially powered for a sample size of 44. We fell far below the recruitment goals, despite 2 years of recruitment, finding a lack of interest for this intervention from the desired patient population. Therefore we consider the feasibility goal to have been a failure. The results should be interpreted with caution as the study was likely underpowered and the real world acceptability of the intervention in the context of this study was not desirable enough to recruit participants.

[figure not shown]
13.2 Baseline values and demographics:

11 subjects completed the Sham treatment and 13 completed the active treatment. No baseline differences in age, body mass index, HAD anxiety, HAD depression, or telomere length were identified between subjects randomized to the sham or active device groups. Both groups had 5 Veterans. Two subjects did not have baseline BMI measured. 1 subject did not have sufficient sample to complete the Telomere length.

No baseline differences were noted in age, BMI, anxiety, depression between Veterans and non-Veterans (all $p > .05$)

13.3 Primary outcome: change in combined HAD score

[figure not shown]
The Active treatment group had a decrease in combined HAD score of 8.8 and in the Sham group the decrease was 3.64 (shown in table); $t=-2.32$, $p=.013$.

13.4 Secondary outcome: Telomeres

13.4.1 Telomere length

No differences in telomere length were noted in pre to post treatment phase, $p=.33$.

13.4.2 Telomerase activity

The results of the telomerase assay showed unacceptably high intra and inter-subject variability, multiple outliers, and non-normal distribution (baseline values skewness 3.1, kurtosis 10.7; end values skewness 2.1, kurtosis 4.1). It is unclear whether this was secondary to natural population variations or assay unreliability but it was determined that analysis of this small sample was unlikely to result in an interpretable finding.

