3.2.2 Biological Measures

The primary biological outcome will be telomerase activity determine using the telomere repeat amplification protocol (TRAP), performed as previously described with minor modification.^{28,29} Isolated PBMC are suspended in Chaps lysis buffer and telomerase extract obtained. Extracts are incubated to build telomere repeats, resulting in the product generated due to telomerase activity. To visualize, the PCR reaction included a labeled primer to amplify signal. The PCR product is then run in an acrylamide gel and detected by fluorescent imaging. Calculation of telomerase product generated (TPG) per 10,000 PBMC is performed using ImageQuant software, which takes the fluorescence intensity within a specified parameter and yields a numerical value representing TPG per 10,000 cells. Telomere length will be determined using real time quantitative polymerase chain reaction (qPCR) methodology as described previously with minor modifications.^{30,31} Peripheral blood mononuclear cells (PBMC) are isolated and genomic DNA extracted. Using the standard curve method, cycle threshold (CT) values are plotted on a standard curve of human genomic DNA to estimate an ng/microliter concentration value. Telomere length values are expressed as the ratio of the estimated concentration generated by PCR of the telomere gene (T) divided by the hemoglobin single (S) copy gene = (T/S).

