10 STATISTICAL ANALYSIS PLAN

10.1 Sample Size

G*Power 3.1 was employed to calculate the number of subjects needed per group to detect a large group differences, slightly less than a 1 standard deviation difference (Cohen's effect, size, $d=.80$) in the effect of daily CES treatment on emotional well-being and PBMC telomerase activity. Based on a one tailed superiority test of improvement (active > sham CES treatment) and an alpha = .05, 22 subjects per group are required to provide adequate statistical power (80%) for the analysis (Noncentrality parameter=2.59, Critical $t(40)=1.68$. To meet this criteria we will include 22 completed subjects per group.

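### Telomerase, the primary biological outcome and one of the two endpoints in the sample-size statement, has no between-group result, and the plan had no rule for skew, outliers or assay failure

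*Combined protocol and SAP*

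**What the plan says.** - **Status.** Section 3.2.2: "The primary biological outcome will be telomerase activity". Section 10.1 bases the sample size on a difference of d = 0.80 "in the effect of daily CES treatment on emotional well-being and PBMC telomerase activity". Section 3.1 predicts a rise at 8 weeks.
- **Planned test.** Section 10.2.2, headed as the secondary outcome, plans one-tailed independent-groups t-tests of whether "participants using the active vs sham CES device will have smaller reductions in telomere length and higher telomerase levels at post compared to pre-treatment". It states no measurement scale, transformation, rank alternative, outlier rule or assay-acceptance limit. Section 10.2 limits the biological analyses to participants with both a pre and a post value.
- **What was reported.** Section 13.4.2 gives skewness 3.1 and kurtosis 10.7 at baseline, and 2.1 and 4.1 at the end. It cites large variability within and between participants, several outliers, non-normality, possible assay unreliability and the small sample, and concludes that "it was determined that analysis of this small sample was unlikely to result in an interpretable finding". There is no result by arm.
- **The other outcomes.** From the same 13 active and 11 sham completers, section 13.3 reports HADS (p = .013) and section 13.4.1 reports telomere length (p = .33).

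**The concern.** A planned, directional, powered hypothesis has no answer, and the decision not to test it followed inspection of the values. Nothing in the plan said in advance when telomerase would be set aside, so the decision rests on judgement after the fact.

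The stated reasons differ in weight. Right skew and outliers are to be expected in a positive intensity measure such as telomerase product per 10,000 cells, and they have standard remedies. Possible assay unreliability is more serious, but section 13.4.2 says it could not tell this from natural variation. At stake is the trial's cellular-health question for the measure it put first among its biological outcomes. Readers, and anyone pooling small trials later, get no estimate at all.

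**Working it through.** **1. The plan's own sample size.** Inputs from section 10.1: d = 0.80, one-tailed alpha 0.05, 80% power, 22 per group, noncentrality 2.59, critical t(40) = 1.68. For two groups, noncentrality = d × √(n₁n₂/(n₁+n₂)) on n₁+n₂−2 degrees of freedom.

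- 21 per group: 0.8 × √10.5 = 2.59, df 40, critical t 1.68, power 81.7%.
- 22 per group: 0.8 × √11 = 2.65, df 42, critical t 1.68, power 83.3%.

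The printed noncentrality and degrees of freedom belong to 21 per group, but 22 is adequate for the stated 80%. The figure is reproduced for practical purposes.

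**2. The number reached.** With 13 and 11 completers: 0.8 × √(143/24) = 1.95, df 22, critical t 1.72, power 59.8% for normal data. This applies equally to every outcome sized at d = 0.80, including HADS, which was reported. Section 13 does not give the number of telomerase pairs, so 13 and 11 is an upper limit.

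**3. Does skew prevent an analysis?** The documents give no telomerase means, SDs or pre–post correlation, so this step is an illustration on assumed inputs. Assume lognormal values. Solving (e^{s²}+2)√(e^{s²}−1) = 3.1 gives a log SD s of 0.73. Assume a true shift of 0.8s on the log scale, pre–post correlation 0.3 to 0.7, no added assay error, and a one-sided test at 0.05. Simulated power at 13 and 11 (40,000 trials per row):

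| Correlation | t-test, raw change | t-test, log change | Log Week 8 adjusted for log baseline |
|---|---|---|---|
| 0.3 | 45% | 48% | 61% |
| 0.5 | 54% | 59% | 69% |
| 0.7 | 70% | 78% | 82% |

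Repeat runs moved the upper figures by up to about 2 points (to 72%, 79% and 83%). Type I error was close to 5% for all three. At correlations 0.3 and 0.5 most of the gain over raw change comes from baseline adjustment (13 of 16 and 10 of 15 points). At 0.7 most comes from the log scale (8 of 12).

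**4. How far that calibration can be trusted.** A log SD of 0.73 makes 3.1 the population skewness. In samples of 24 from that distribution the average sample skewness is only about 1.6, and 3.1 or more occurs in about 5–7% of samples. The real distribution may be heavier-tailed. With log SD 1.0 to 1.25 and an effect of 0.8 SD of log change, power at 13 and 11 is 37–50% for raw change, 60% for log change and 53–60% for a rank test on raw change.

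**5. Adding assay error.** If only half, or only 30%, of the observed log-scale variance were true signal (assumed; not in the documents), power for the adjusted log analysis at correlation 0.5 falls to about 38% or 26%. Its type I error stays near 5%. Under these assumptions, noise unrelated to arm costs precision but does not create a false effect.

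**The case against.** The strongest defence is that the team did not hide anything. Section 13.4.2 states openly that telomerase was not analysed, gives five reasons and shows the shape statistics at both time points. If the assay was unreliable, no transformation repairs it, and step 5 shows that power could then be very low. This is also a self-declared feasibility failure, and section 10.2.2 ranks telomerase as secondary. All of that stands. It limits what a result could show, but does not explain why none is given when telomere length, which section 14 itself calls difficult to interpret, was reported.

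Two stronger readings are tempting, and the documents support neither.

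- *The omission happened because the plan offered only a raw-scale t-test.* Section 13.4.2 never cites the planned test, and section 10.2.2 states no scale. Non-normality is one reason among several.
- *This is selective reporting of an unwelcome result.* The statistics shown are by time point, not by arm, and nothing indicates that a group comparison was run. Section 4.4 keeps the device code sealed until data collection ends, but no section says whether the telomerase decision was made blind to allocation. The documents neither establish nor exclude an outcome-driven choice.

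It would also be too strong to call a late analysis unbiased. Section 10.2 restricts it to participants with both samples, and section 5.3 makes the final visit conditional on compliance, so it compares completers. Section 7.2 has baseline blood drawn after the first one-hour device session, so the baseline is not strictly pre-treatment.

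**Conclusion.** The concern holds as a gap in reporting and in pre-specification. A named primary biological outcome, included in the sample-size statement, has no between-group result, and the plan had no rule for skew, outliers or assay failure. Skew and outliers are not grounds for omission, unproven assay noise is a reason for a caveat, and the small sample applied equally to outcomes that were reported.

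The size of the loss is uncertain. The power figures are illustrative. They rest on an assumed lognormal shape, effect and correlation, and the headline range assumes no added assay error. They show that a workable analysis existed, not that it would have been decisive: 80% power at 13 and 11 is reached only at the top of the assumed range. The HADS primary outcome is unaffected. This should be corrected, but it does not undermine the trial's main result.

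**What to change.** In section 10.2.2, add a dated analysis marked as post hoc: log telomerase at Week 8 adjusted for log baseline, reported as a ratio of geometric means (active to sham) with its confidence interval, with a rank test on change as a check. State how any zero value would be handled before taking logs.

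In section 13.4.2:
- Report that result for all participants with both samples, with the number of pairs per arm.
- Give any replicate data that exist. The documents do not say whether replicates were run.
- State whether the decision not to analyse was made before or after the device code was opened.
- Label the result post hoc, completer-only and low reliability, and note that the baseline sample followed the first device session.

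The cost is one analysis and a short table on existing data. The downside is a wide interval that needs an assay caveat and may be over-read without it.

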13.5 Exploratory outcomes

These outcomes were not measured due to the lower than expected sample size.

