3 OBJECTIVES

3.1 Study Objectives

We anticipate significant improvements in emotional well-being associated with eight-weeks of daily CES treatment. Scores on the individual and combined anxiety and depression subscales of the HADS will decrease. Improvements in other aspects of mental health (measured with the MHC-SF) are expected as a secondary effect of the improved negative affect measured in the HADS. An increase in telomerase is expected at 8 weeks. In addition we expect improvements in the PROMIS measures of fatigue, sleep disturbance, and pain interference.

Biological samples will be retained for measurement of additional inflammatory gene regulation pathways in peripheral immune cells if additional funding can be obtained for processing and analysis of the samples. We anticipate that inflammatory gene profiles would be improved in subjects who have improved emotional wellbeing with CES treatment.

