7.2 Enrollment/Baseline Screening (Visit 1)

This visit will occur at the Oppenheimer Family Center for Neurobiology of Stress. It will take about 3 hours to complete the screening and device training process. The research team will verify OEF/OIF Veteran status (i.e. DD 214) before study enrollment if the subject identifies as a Veteran. The potential subjects will first review and sign ICF and HIPAA Authorization with either the RN, FNP, or MD. All are certified to obtain informed consent (nursing or physician license). Subjects will be identified by the PI, [name], as possibly eligible after the clinic visit and the study questionnaires have been completed and scored. Medical history will be reviewed and a physical will be performed as well. The assessment questionnaires include:

- A standardized psychiatric evaluation (MINI)
- Hospital Anxiety and Depression Scale (HADS)
- Mental Health Continuum Short Form (MHC-SF)
- Patient Reported Outcomes Measurement Information System (PROMIS-29)
- Positive and Negative Affect Schedule Short Form (PANAS-SF)
- Connor-Davidson Resilience Scale (CD-RISC)
- Perceived Stress Scale (PSS)
- Patient Health Questionnaire (PHQ)

-
- Columbia-Suicide Severity Rating Scale (C-SSRS) Self Report Screener - Recent

We will use the HADS to assess symptom severity defined as normal range (0-7), mild (8-10), moderate (11-14) or severe (15-20). Subjects with impaired emotional wellbeing as defined as a minimum combined HADS score of 14 will be included. Subjects who score >15 will be excluded in the study and will be given referrals to their personal provider or community mental health resources. (See “Reporting Suicidal Ideation” Section 5.4)

Subjects who express interest in participating and meet the inclusion criteria will be trained to use the CES device. They will be instructed that the device is set to a low level that should not be detectable. Subjects will have their first 1 hour treatment at OCNS (commencing Week 1 of the study). Subjects who tolerate the device treatment will then have blood drawn for baseline biological measures. They will be informed that this is a randomized controlled trial and they may or may not have an active device kit. Subjects will be sent home with a device, instructions for daily treatment, and a patient diary to track usage and side effects if applicable.

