7.3 Intermediate Study Visit (Visit 2)

This visit will occur at the Oppenheimer Family Center for Neurobiology of Stress. This visit will take approximately 1 hour and will occur Week 4 ± 1 week. Subjects must complete this set of study questionnaires:

- Hospital Anxiety and Depression Scale (HADS)
- Positive and Negative Affect Schedule Short Form (PANAS-SF)
- Perceived Stress Scale (PSS)
- Columbia-Suicide Severity Rating Scale (C-SSRS) Self Report Screener - Since Last Contact
- Patient Reported Outcomes Measurement Information System (PROMIS-29)

Subjects will have vital signs and weight measured by a nurse. Adverse events and concomitant medication report will be collected as well. The study coordinator will collect the tracking diary for weeks 1-4 and provide another tracking diary to complete for weeks 5-8.

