7.4 Final Study Visit (Visit 3)

This visit will occur at the Oppenheimer Family Center for Neurobiology of Stress. This visit will take approximately 2 hours and will occur after 8 weeks of

treatment, Week 8 + 1 week. Subjects will be asked to bring the CES device to return. The study coordinator will collect the tracking diary for weeks 5-8. The subjects must complete the final set of questionnaires:

- Mini International Neuropsychiatric Interview (MINI)
- Hospital Anxiety and Depression Scale (HADS)
- Mental Health Continuum Short Form (MHC-SF)
- Patient Reported Outcomes Measurement Information System (PROMIS-29)
- Positive and Negative Affect Schedule Short Form (PANAS-SF)
- Connor-Davidson Resilience Scale (CD-RISC)
- Perceived Stress Scale (PSS)
- Patient Health Questionnaire (PHQ)
- Columbia-Suicide Severity Rating Scale (C-SSRS) Self Report Screener - Since Last Contact
- Impression of Global Improvement Scale

The subjects will have vital signs and weight measured and have the final blood draw performed by a nurse. Adverse events and concomitant medication report will be collected as well.

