8 STUDY PROCEDURES/EVALUATIONS

8.1 Study Procedures/Evaluations

Electronic assessment questionnaire data will be collected from subjects during the visits at UCLA OCNS using SurveyMonkey (www.surveymonkey.com) and unique subject identifiers. Survey Monkey states they utilize some of the most advanced technology for Internet security commercially available today. Unique usernames and passwords are required and must be entered each time a user logs on. When a user accesses secured areas of our site, Secure Sockets Layer (SSL) technology protects user information using both server authentication and data encryption, ensuring that user data is safe, secure, and available only to authorized persons. Servers are kept in a locked cage. Digital surveillance equipment monitors the data center. A firewall restricts access to all ports except 80 (http) and 443 (https). Intrusion detection systems and other systems detect and prevent interference or access from outside intruders. QualysGuard network security audits are performed weekly. McAfee SECURE scans performed daily.

The subjects will complete the aforementioned study questionnaires above (see “Study Schedule” Section 7) and the assessments will be scored per published guidelines.

All paper source data collected at UCLA will only contain unique subject ID numbers. Research staff will know matching of ID with subject for data collection purposes but this will not be written on documents in the field. The documents will be coded before being stored in subject’s file. Files will be secured in a locked cabinet in a locked room.

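### Section 13.5's reason for having no exploratory results does not fit the visit schedule, so every planned behavioural outcome except HADS is unreported without a valid reason

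*Combined protocol and SAP*

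**What the plan says.** Section 10.2.3 commits to a one-sided between-group test of each exploratory scale, with this as the hypothesis: "active CES device will be superior to sham in improvement of PROMIS domains, MHC-SF, CD-RISC, PSS, PHQPANAS-SF and impression of global improvement". I read the run-together term as PHQ and PANAS-SF, which makes seven instruments, and I take the PROMIS domains to come from the PROMIS-29 listed in section 7. Section 10.2 adds that behavioural measures will be analysed both by intention to treat and in completers.

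Collection is built into the visits. At Visit 1 (7.2), possible eligibility is judged "after the clinic visit and the study questionnaires have been completed and scored". At Visit 2 (7.3): "Subjects must complete this set of study questionnaires". At Visit 3 (7.4): "The subjects must complete the final set of questionnaires". Section 8.1 puts all of them in one system, "Electronic assessment questionnaire data will be collected from subjects during the visits at UCLA OCNS using SurveyMonkey", and says they will be scored. Section 5.3 ties the Visit 2 and final payments partly to questionnaire completion.

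Among the objectives (3.1), improvement is predicted for MHC-SF and for part of PROMIS: "In addition we expect improvements in the PROMIS measures of fatigue, sleep disturbance, and pain interference".

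The whole of section 13.5 is one sentence: "These outcomes were not measured due to the lower than expected sample size". Section 13.3 reports HADS, 13.4.1 reports telomere length, and 13.4.2 describes the telomerase data and says why they were not tested.

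**The concern.** Sample size is a property of the finished trial, whereas measurement happens subject by subject. A shortfall can justify not testing an outcome, or reading it cautiously. It does not by itself explain why an instrument listed beside HADS produced nothing from a subject who completed HADS at that visit.

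The interpretation in section 14 is what is at stake. It takes the HADS difference as support for a possible benefit on negative affect in young men. PANAS-SF is a direct measure of affect and is scheduled at all three visits. PHQ, PSS and the global improvement scale also bear on the question. With none of them shown, a reader cannot tell whether they agree with HADS, disagree with it, or do not exist.

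**Working it through.** **Step 1. Match instruments to visits** (sections 3.2.1, 7.2–7.4, 10.2.3).

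| Instrument | Visit 1 | Visit 2 | Visit 3 |
|---|---|---|---|
| HADS (primary, reported) | yes | yes | yes |
| PROMIS-29 | yes | yes | yes |
| PANAS-SF | yes | yes | yes |
| PSS | yes | yes | yes |
| MHC-SF | yes | no | yes |
| CD-RISC | yes | no | yes |
| PHQ | yes | no | yes |
| Global improvement | no | no | yes |
| PCL-M (3.2.1 only) | no | no | no |

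The seven instruments of 10.2.3 account for 6 + 3 + 7 = 16 scheduled administrations per completing subject. No result from any of them appears. PCL-M is called an exploratory outcome in 3.2.1 but is in no visit list and not in 10.2.3, so the schedule argument does not cover it.

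**Step 2. Reproduce the plan's sample size** (10.1: d = 0.80, one-sided alpha .05, 80% power, 22 per group). Noncentrality = d / sqrt(1/n1 + 1/n2).
- 22 per group: 0.80 / sqrt(2/22) = 2.65, df 42, power 83.3%. The stated 22 is sufficient.
- The printed 2.59 and df 40 belong to 21 per group: 0.80 / sqrt(2/21) = 2.59, power 81.7%. The discrepancy is minor.
- Achieved 13 versus 11 (13.2): 0.80 / sqrt(1/13 + 1/11) = 0.80 / 0.410 = 1.95, df 22, power 59.8%.

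Power therefore fell from 83.3% to 59.8%. That is a reason for caution with tests. It applies in the same way to HADS, which was tested.

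**Step 3. Precision available for an exploratory scale.** With complete data on 13 and 11 subjects, the 95% CI half-width in SD units is t(.975, 22) × sqrt(1/13 + 1/11) = 2.074 × 0.410 = 0.85 SD.

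**Step 4. Compare with HADS** (13.3: decreases of 8.8 and 3.64, |t| = 2.32). Treating this as an ordinary two-sample t on 22 df:
- Difference = 8.8 − 3.64 = 5.16 points.
- Standard error = 5.16 / 2.32 = 2.22 points; implied SD = 2.22 / 0.410 = 5.43 points.
- Half-width = 2.074 × 2.224 = 4.61 points, so the CI is roughly 0.55 to 9.77 points. In SD units, 4.61 / 5.43 = 0.85.

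The two half-widths agree because both depend only on the group sizes. The comparison shows only that precision gives no ground for treating the exploratory scales differently from HADS; it does not measure bias. One caveat: on 22 df the one-sided p for 2.32 is .0150, not the reported .013, so the reported test may have used other degrees of freedom, perhaps from the planned mixed model.

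**Step 5. Multiplicity if all seven were tested.** 10.2.3 has no adjustment. Seven independent one-sided tests at .05 give 1 − 0.95^7 = 0.30 familywise error. This argues against significance claims but not against descriptive estimates.

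**The case against.** The strongest reply is that the shortfall was not a surprise at the end. Sections 2.1 and 4.2 show that recruitment difficulty was recognised during the study: eligibility was widened to non-Veterans, recruitment was extended, and enrolment was capped for lack of resources. The team could have dropped secondary questionnaires on the way. Section 13.4.2 lends this some weight, because it shows the report describing an outcome as measured but not tested when that was the case. I accept that literal non-collection is possible. It would still be a departure from 7.3 and 7.4, whose lists still carry the instruments, and 13.5 does not declare it as one.

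Second, leaving out seven unadjusted tests in 24 subjects is defensible. That stands for the tests, but it does not cover the absence of counts and summaries.

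Third, the wording in 7.2 is softer than in the later visits, and 3.1 predicts improvement only for MHC-SF and three PROMIS domains among the exploratory measures. Both points are correct. The remaining hypotheses come from 10.2.3 alone, and mandatory completion is explicit only at Visits 2 and 3.

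A reader might infer that results were withheld so that the one favourable outcome could stand alone. The documents do not support that. They do not establish that the data exist. HADS is the prespecified primary outcome (3.2.1, 10.2.1). A null telomere length result (p = .33), an unusable telomerase assay and a failed feasibility goal are all disclosed, with advice to interpret the results cautiously (13.1). Section 13.5 itself tells the reader that the exploratory results are missing.

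**Conclusion.** The contradiction stands. Section 13.5 gives a reason that does not account for the absence of questionnaires scheduled in the same visits as HADS, so the seven instruments planned in 10.2.3 are unreported without a valid explanation. This is incomplete reporting; results-driven selection is not shown. Two readings remain open, collected but not analysed, or dropped without declaration, and the documents do not decide between them.

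The effect on the trial's findings cannot be quantified without the data. If the data are complete, each missing between-group estimate would carry a half-width of about 0.85 SD: imprecise, but on the same footing as the reported HADS result. That figure assumes 13 and 11 subjects with change scores on each scale, and for the global improvement scale, which is taken once, a single Visit 3 score. Fewer available scores would widen it. The conclusion also rests on the section 7 lists being the schedule in force.

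**What to change.** Replace section 13.5 with a statement of which instruments were collected, giving the number per arm at each visit.
- **Collected:** one table with n, mean change by arm (score by arm for global improvement), between-group difference and 95% CI, labelled exploratory and without significance claims. State whether the set is intention to treat or completers, since 10.2 promises both.
- **Not collected:** declare a protocol deviation, with the visits affected and the actual reason.
- **PCL-M:** reconcile 3.2.1 with section 7 and 10.2.3, and say whether it was ever administered.
- **Section 14:** until this is done, add a sentence saying that the conclusion on affect rests on HADS alone.

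If the data exist, the cost is one descriptive table. If they do not, it is a short corrected statement. No new data collection is needed in either case.
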